In this small pilot study we were unable to achieve all of our primary and secondary endpoints. Additionally, interventions in low grade injuries are uncommon, and a larger data set would allow for delineation in management between low, moderate and high grade splenic and hepatic injuries. This study did not have power due to a limited number of patients receiving interventions, thus making characterization of types of interventions and final outcomes difficult.

A large multicenter trial would allow for appropriate power for the study and thus allow for us to meet our endpoints. There are multiple variables affecting the management of blunt splenic and hepatic injuries and currently no clear guidelines exist in regards to repeat imaging. Gaining a better understanding of types of delayed complications, how they present, and current management strategies would assist in creating a standardized algorithm in the treatment of this patient population.

Specific Aims of Multicenter Study

Aim 1: To define which blunt splenic and hepatic injuries are at risk of delayed complications in order to develop a societal management guideline.

Aim 2: To ascertain which patients warrant repeat imaging and when this imaging should be performed.

Aim 3: To define what interventions are needed based upon delayed complications found radiographically.

Aim 4: To analyze 30 day readmission rates to the hospital due to spleen and/or liver injury.

Methods

This will be a retrospective observational study. Patients will be managed according to the surgeon's discretion. The study will enroll a total of 5,000 subjects at minimum. This study plans to enroll 200 patients at our institution, Penn Medicine Lancaster General Health. The number of subjects that will be enrolled at each additional participating site is 200.

Inclusion Criteria:

• All patients (all ages) who present with blunt trauma to the spleen and/ or liver

Exclusion Criteria:

- Patients who suffer a penetrating mechanism
- Patients transferred out to another facility prior to admission

Updated Terms/Definitions:

• **Clinical Change (CC) (to replace Physician Discretion)**- repeat imaging prompted by patient factors including vital sign changes, lab abnormalities, abdominal pain, and patient symptoms

• Non Clinical Change (NCC) (to replace Standard Protocol)- repeat imaging prompted by institutional protocol/ recommendations, individual physician practice pattern, or that performed on a scheduled basis

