The time frame for data query will be from IRB approval (2020) until December 31, 2023. The electronic medical record (EMR) may be used in order to identify participants who match study defined demographic criteria.

Primary Outcome: Delayed complications found on repeat imaging

Secondary Outcomes: Timing to repeat imaging/ intervention, interventions performed based on complications found, mortality, length of stay, blood transfusion requirements, VTE prophylaxis, and 30 day readmission variables [readmission within 30 days for spleen and/or liver injury, readmission CT scan, interventions performed].

Variables

List specific variables to be collected & analyzed: Age, sex, time from injury, Injury Severity Score (ISS), Abbreviated Injury Scale (AIS), Trauma and Injury Severity Score (TRISS), mechanism of injury, initial vital signs, anticoagulant use and reversal agents, initial and repeat imaging, grade of organs injured, complications found, details regarding initial and any delayed interventions, blood transfusions, details regarding venous thromboembolism prophylaxis, venous thromboembolism complications, hospital length of stay, intensive care unit length of stay, mortality, and 30 day readmission variables [readmission within 30 days for spleen and/or liver injury, readmission CT scan, interventions performed].

Data Collection and Statistical Analysis

Standardized data will be collected for each patient meeting inclusion criteria (see data collection tool). The de-identified data for each patient will be entered into a secure REDCap database. A total of 5,000 patients (3,500 splenic injuries and 1,500

hepatic injuries) is recommended to identify a significant difference between the non clinical change and clinical change group. Complications found on repeat imaging will be assessed using univariate and multivariate analysis.

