Categorical variables will be compared using Fisher's exact test or Chi-squared test. Continuous variables will be assessed using Student's t-test. For multivariate analysis, a mixed effect multinomial logistic regression will be run with a binary outcome of whether the patient had a delayed complication. Another mixed effect multinomial logistic regression will be run with a binary outcome of whether the patient had an intervention performed. Additional analysis will be completed to determine if there is optimal timing for repeat imaging to identify complications. Data will be reported as adjusted odds ratios with 95% confidence intervals. Statistical significance will be defined by a p<0.05.

Sample Size and Power Estimates

A retrospective pilot study was completed with 235 patients with splenic injuries and 365 hepatic injuries. Of the patients with splenic injuries, 105 underwent repeat imaging, 46 had organ specific complications, and 16 had an intervention performed. Of the patients with hepatic injuries, 122 underwent repeat imaging, 30 had organ specific complications, and 12 had an intervention performed.

Spleen Power Analysis

Combined complication rate for patients who had repeat imaging: 46/105 = 0.44Standard protocol complication rate: 18/38 = 0.47Physician discretion complication rate: 28/67 = 0.42

Complication Rate:	Complication Rate:	Odds Ratio	Sample Size
Standard protocol	Physician discretion		(Total Population)
0.46	0.43	0.89	8,614
0.47	0.42	0.82	3,100
0.48	0.41	0.75	1,582

Liver Power Analysis

Combined complication rate for patients who had repeat imaging: 30/122 = 0.25Standard protocol complication rate: 10/50 = 0.20Physician discretion complication rate: 20/72 = 0.27

Complication Rate: Standard protocol	Complication Rate: Physician discretion	Odds Ratio	Sample Size (Total Population)
0.21	0.26	1.32	2,256
0.20	0.27	1.48	1,150
0.19	0.28	1.66	696

Consent Procedures

This is a retrospective observational study in which data will be retrospectively recorded on patients according to institutional protocols. Data will be input into REDcap database without any patient identifiers. Thus, a waiver of consent is requested.

Confidentiality and Privacy

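### The 3,500 spleen / 1,500 liver split behind the 5,000 total is not secured by any enrolment rule; at the pilot's organ mix, the 5,000 minimum would leave the spleen comparison at about 60% power

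*Supplement*

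**What the plan says.** Under Data Collection and Statistical Analysis the protocol recommends "A total of 5,000 patients (3,500 splenic injuries and 1,500" hepatic injuries, to detect a difference between the non-clinical-change and clinical-change groups. The two parts add to exactly 5,000, so the split counts each patient under one organ only.

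Methods sets the enrolment: "The study will enroll a total of 5,000 subjects at minimum". The lead site plans 200, and "The number of subjects that will be enrolled at each additional participating site is 200". Eligibility is "All patients (all ages) who present with blunt trauma to the spleen and/ or liver". The two exclusions (penetrating mechanism, transfer out before admission) do not depend on which organ is injured. No quota, cap or closure rule by organ is given.

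Sample Size and Power Estimates starts from the pilot: "A retrospective pilot study was completed with 235 patients with splenic injuries and 365 hepatic injuries". Its spleen table has three scenarios. The one at the observed pilot rates reads "0.47 0.42 0.82 3,100" (standard protocol rate, physician discretion rate, odds ratio, total). The corresponding liver row, 0.20 v 0.27, asks for 1,150.

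**The concern.** The spleen has the smaller planned difference (5 points, against 7 for liver) and so needs the larger sample. The plan allots it 70% of the total. In the sponsor's own pilot, spleens were the minority of injuries, and taking all comers does nothing to reverse that. The 5,000 counts patients of either kind, so the minimum can be met with far fewer spleens than the power table asks for and a large surplus of livers.

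At stake is how a null spleen result would be read. The first aim is a management guideline. A non-significant comparison at about 60% power could be taken to show that the reason for re-imaging makes no difference to the complications found, in a study whose protocol presents its size as sufficient.

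**Working it through.** **Inputs**
- Pilot: 235 splenic and 365 hepatic injuries, 600 in all (Sample Size and Power Estimates).
- Target: 5,000 = 3,500 + 1,500 (Data Collection and Statistical Analysis).
- Spleen rates 0.47 v 0.42; liver rates 0.20 v 0.27 (power tables).
- Significance: "Statistical significance will be defined by a p<0.05". Sidedness, power and allocation are not stated.

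**1. Reproduce the plan's figures.** With two-sided 5%, 80% power, 1:1 groups and no continuity correction, where p̄ is the mean of p1 and p2:

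n per group = [1.96·√(2p̄(1−p̄)) + 0.8416·√(p1(1−p1) + p2(1−p2))]² / (p1−p2)²

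Spleen, p̄ = 0.445: n = 1,549.6, rounded up to 1,550, total 3,100. Liver, p̄ = 0.235: n = 574.8, rounded up to 575, total 1,150. All six rows of the two tables match exactly (8,614, 3,100, 1,582; 2,256, 1,150, 696), so 80% power and 1:1 allocation are inferred from that match.

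**2. Organ numbers at the pilot mix, no overlap**
- Spleen: 5,000 × 235/600 = 1,958, which is 56% of 3,500 and 63% of 3,100.
- Liver: 5,000 × 365/600 = 3,042.

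**3. Power on the table's basis**

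| Spleens | 0.47 v 0.42 | 0.48 v 0.41 |
|---|---|---|
| 3,500 | 84.6% | 98.7% |
| 3,100 | 80.0% | 97.5% |
| 1,958 | 60.5% | 87.7% |

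At the pilot's 38:67 group ratio, 1,958 spleens give 57.3% for 0.47 v 0.42. With 1,958 spleens in equal groups, the smallest difference detectable with 80% power is about 6.3 points. Liver power at 0.20 v 0.27 is 89.3% at 1,500 and 99.5% at 3,042.

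**4. Patients with both injuries.** The data dictionary allows them, but the pilot overlap is not given. If b pilot patients had both, there were 600 − b patients, and spleens = 5,000 × 235/(600 − b). Equivalently, if a share B of patients has both, spleens = 5,000 × (1 + B) × 235/600.
- B = 10%: 2,154 spleens, 64.6% power.
- B = 20%: 2,350 spleens, 68.4% power.
- b = 221 (94% of spleen patients): 5,000 × 235/379 = 3,100, 80% power.
- b = 235 (every spleen patient): 5,000 × 235/365 = 3,219, 81.5% power. This is the maximum at the pilot mix, so 3,500 is out of reach from 5,000 patients.

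**5. A different spleen share among the 5,000**
- 45% (2,250 spleens): 66.5%.
- 50% (2,500): 71.1%.
- 60% (3,000): 78.7%.
- 62% (3,100): 80.0%.

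**6. Patients needed at the pilot mix, no overlap.** 3,100 ÷ (235/600) = 7,915; 3,500 ÷ (235/600) = 8,936.

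**7. Keeping the re-imaging fraction apart.** The tabulated rates are among re-imaged patients: "Of the patients with splenic injuries, 105 underwent repeat imaging, 46 had organ specific complications, and 16 had an intervention performed". With 105/235 = 44.7% re-imaged, 3,500 spleens leave 1,564 (51% power) and 1,958 leave 875 (32%). On that count the mix accounts for the step from 51% to 32%; the step from 85% to 51% is a separate shortfall.

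**The case against.** Several stronger readings are tempting, and the documents do not support them.

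- *The plan predicts 3,500 spleens and is wrong.* It recommends that number. It is a requirement, in line with the tabulated 3,100 and 1,150 with a margin, and not a forecast of case mix. The gap is that nothing in the enrolment rule secures it.
- *The study will bring only about 1,960 spleens.* That holds only if the pilot mix carries over. The pilot covered adults at two institutions; this study is multicentre and takes all ages. The pilot figure also counts injuries rather than patients, with unknown overlap. The direction is robust, since 80% power needs a spleen share near 62% or almost complete overlap, but the single figure is not.
- *The target cannot be met.* The 5,000 is a minimum, and the plan does not forbid enrolling the 7,900 or so that would give 3,100 spleens. What stands is that no rule makes enrolment continue until then.
- *The spleen comparison is underpowered in every scenario.* It is not. About 1,960 spleens exceed the 1,582 in the 0.48 v 0.41 row, where power is about 88%. The 3,500, however, fits the 0.47 v 0.42 row, which holds the observed pilot rates.
- *The mix cuts power from 85% to 32%.* This combines two defects, as step 7 shows.

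It is also fair to say that the study is observational, with mainly descriptive aims, and that the shortfall touches one organ's comparison. That limits the consequence. It does not mend a stated size basis that the only available mix contradicts.

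**Conclusion.** The point holds in conditional form. The 70:30 split is unexplained, runs opposite to the only mix in the documents, and is not tied to enrolment or closure. If the pilot mix applies to the 5,000-patient minimum, spleen power at 47% v 42% is about 60% with no overlap and 65-68% if 10-20% of patients have both injuries, against 80% at the tabulated 3,100. For spleen shares of 45% to 60% it is 67% to 79%. Liver power is above 99%.

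This rests on two-sided 5%, 1:1 groups and 80% power, all inferred because they reproduce every table row; on counting every injury, as the plan's split does; and on the pilot mix or the stated alternatives to it. The 10-20% overlap is an assumption.

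**What to change.** Keep 3,100 spleens and 1,150 livers as the requirements from the power tables. Replace the statement equating 5,000 patients with 3,500 splenic and 1,500 hepatic injuries by the organ numbers expected from 5,000 all-comers. State these as conditional on the pilot mix (about 1,960 and 3,040 with no overlap), with a range for the spleen share and for patients with both injuries. Give the spleen and liver power at those numbers, and state the power level, sidedness and allocation used.

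The cost is protocol wording and a less favourable spleen power figure. No extra patients are needed.

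### No adjusted analysis is planned for mortality, length of stay, transfusion, VTE prophylaxis or readmission, so crude differences by imaging reason may reflect case mix, in either direction

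*Supplement*

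**What the plan says.** The protocol appears twice in the Supplement, with the same text on this point.

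- **Design (Methods).** "This will be a retrospective observational study. Patients will be managed according to the surgeon's discretion".
- **Groups (Updated Terms/Definitions).** CC is "repeat imaging prompted by patient factors including vital sign changes, lab abnormalities, abdominal pain, and patient symptoms". NCC is "repeat imaging prompted by institutional protocol/ recommendations, individual physician practice pattern, or that performed on a scheduled basis".
- **Contrast the study is sized for (Data Collection and Statistical Analysis).** The sentence giving the 5,000 target (3,500 splenic, 1,500 hepatic) ends: "hepatic injuries) is recommended to identify a significant difference between the non clinical change and clinical change group".
- **Secondary outcomes.** Besides timing, the list runs: "interventions performed based on complications found, mortality, length of stay, blood transfusion requirements, VTE prophylaxis, and 30 day readmission variables".
- **Crude tests.** "Categorical variables will be compared using Fisher's exact test or Chi-squared test. Continuous variables will be assessed using Student's t-test". These sentences do not name the groups compared.
- **Adjusted models.** There are two mixed-effects logistic regressions, one for delayed complication and one for intervention performed. The same section mentions univariate and multivariate analysis for complications found on repeat imaging only. A later sentence says results will be given as adjusted odds ratios with 95% confidence intervals. It names neither outcome nor covariate.
- **Severity data (Variables; data collection tool).** "Injury Severity Score (ISS), Abbreviated Injury Scale (AIS), Trauma and Injury Severity Score (TRISS), mechanism of injury, initial vital signs" are collected, as are age, GCS, organ grade and anticoagulant use.

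**The concern.** Five secondary outcomes have no named adjusted analysis. The one group contrast that the protocol describes is between patients sorted by why they were re-imaged, not by chance. One group is defined by the patient's condition, the other by protocol, habit or schedule. If the two differ in injury severity on arrival, a crude difference in deaths, days in hospital or units transfused mixes that case mix with anything due to imaging reason.

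This matters because Aim 1 is to inform a management guideline, and the Background already draws practice suggestions from pilot contrasts with no adjustment mentioned. A crude secondary result could be used in the same way. Mending site clustering or skewness would not help: a site intercept or a rank test leaves a severity imbalance within sites untouched.

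**Working it through.** **1. The plan's own figures.** The power tables follow from an unadjusted two-proportion formula (two-sided 0.05, 1:1 allocation, and 80% power, which is assumed because none is stated):

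n per group = [1.96·√(2p̄(1−p̄)) + 0.8416·√(p₁(1−p₁)+p₂(1−p₂))]² / (p₁−p₂)²

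- Spleen, 0.47 v 0.42: 1,549.6, rounded up to 1,550; total 3,100, as printed.
- Liver, 0.20 v 0.27: 574.8, rounded up to 575; total 1,150, as printed.

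The other four rows also reproduce. So the CC v NCC contrast is sized on complication rate alone. The tables say nothing about the other outcomes.

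**2. Which method reaches which outcome**

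| Outcome | Adjusted model named | Crude test available |
|---|---|---|
| Delayed complication | yes | yes |
| Intervention performed | yes | yes |
| Mortality, VTE prophylaxis, 30-day readmission | no | chi-squared or Fisher |
| Length of stay, transfusion volume | no | Student's t-test |

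**3. Group sizes at pilot rates** (standard protocol taken as NCC, physician discretion as CC)

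- Spleen: 3,500 × 105/235 = 1,564 re-imaged; NCC × 38/105 = 566, CC × 67/105 = 998.
- Liver: 1,500 × 122/365 = 501 re-imaged; NCC × 50/122 = 205, CC × 72/122 = 296.
- Pooled: NCC 771, CC 1,294. This is approximate, since the form allows a patient to have both injuries.

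**4. Mortality with no true effect of imaging reason.** Severity shares and death rates are assumptions. With severe share s, crude rate = s·m(severe) + (1−s)·m(not severe). With d the difference in crude rates, SE = √[p_N(1−p_N)/n_N + p_C(1−p_C)/n_C], and P(p<0.05) = Φ(d/SE − 1.96) + Φ(−d/SE − 1.96).

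| Death rate, severe / not | Severe share, NCC / CC | Crude death, NCC / CC | Crude OR | P(p<0.05) pooled | Spleen | Liver |
|---|---|---|---|---|---|---|
| either pair | 40% / 40% | equal | 1.00 | 5% | 5% | 5% |
| 10% / 2% | 40% / 50% | 5.2% / 6.0% | 1.16 | 12% | 10% | 7% |
| 10% / 2% | 40% / 60% | 5.2% / 6.8% | 1.33 | 33% | 26% | 12% |
| 10% / 2% | 40% / 30% | 5.2% / 4.4% | 0.84 | 13% | 11% | 7% |
| 15% / 3% | 40% / 50% | 7.8% / 9.0% | 1.17 | 16% | 13% | 8% |
| 15% / 3% | 40% / 60% | 7.8% / 10.2% | 1.34 | 47% | 37% | 15% |
| 15% / 3% | 40% / 30% | 7.8% / 6.6% | 0.84 | 17% | 14% | 8% |

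The severity-stratified odds ratio is 1.00 in every row. If the null variance is pooled, as in a chi-squared test, the pooled-organ range for the rows with CC more severe is 11 to 44% instead of 12 to 47%.

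**5. Length of stay, organs pooled.** Assume severe patients stay D = 5 to 7 days longer, with a within-stratum SD of 8. Spurious difference = (s_C − s_N)·D; group variance = 64 + D²·s(1−s).

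- D = 5, 40% v 50%: 0.5 days; SE = √(70/771 + 70.25/1,294) = 0.381; p<0.05 in 26%.
- D = 7, 40% v 60%: 1.4 days; SE = √[75.76 × (1/771 + 1/1,294)] = 0.396; p<0.05 in 94%.
- A reversed 10-point imbalance gives −0.5 to −0.7 days.

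**The case against.** **The contrast is not stated for these outcomes.** The test sentences name no groups, and no aim asks for mortality or stay by imaging reason. Aim 4, on readmission rates, could be purely descriptive. This stands: CC v NCC is an inference from the sample-size sentence and the power tables, so the point is conditional on that comparison being made.

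**The reporting sentence may promise adjustment.** The sentence on adjusted odds ratios could be stretched to binary outcomes such as death or readmission. But it follows directly on the two named models and lists nothing further, and an odds ratio cannot serve length of stay or transfusion volume. The gap is firm for the continuous outcomes and somewhat weaker for the binary ones.

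**The direction is unknown.** A reader might infer that CC patients arrive sicker, so that crude results will look worse after CC imaging and favour protocol imaging. The documents do not support this. CC is defined by what prompts the repeat scan, not by severity on arrival. NCC includes protocol imaging, and the Background notes that some studies recommend follow-up imaging only for high-grade injury, which could make NCC the more severe group. In the pilot spleen data, complications (47% v 42%) and interventions for them (56% v 21%) were higher under standard protocol. Those are not admission severity, but they give no support to a predicted sign.

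**Adjustment is limited.** Admission covariates cannot remove confounding by the later clinical change, and deaths and readmissions may be too few for a long list. The data dictionary also gives no timing for ISS. All three points stand and shape the fix.

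**Conclusion.** The concern holds in a conditional form. Mortality, length of stay, transfusion, VTE prophylaxis and 30-day readmission are reached only by crude tests. If they are compared by imaging reason, a difference in case mix may be read as an effect of imaging reason. The sign cannot be predicted.

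Under the assumed severity mix and death rates, the spurious mortality odds ratio is modest, but false-positive rates rise well above 5% with organs pooled, and less in liver alone. Length of stay is more exposed. Every one of these sizes rests on assumed severity shares, outcome rates and SD, and on pilot re-imaging rates carrying over. With no imbalance the excess is nil. The documents do not say how these secondary results will be interpreted, so a misleading reading is a risk, not a certainty. The point concerns secondary outcomes; the primary outcome has a mixed-effects model.

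**What to change.** In Data Collection and Statistical Analysis:

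1. State whether these outcomes will be compared by CC v NCC. If not, say that they are descriptive.
2. If they will, report each comparison from a mixed-effects regression with a site intercept, of a type suited to the outcome, with its estimate and 95% confidence interval.
3. Adjust for admission covariates already collected: age, ISS, organ grade, GCS, SBP and anticoagulant use. For rare outcomes such as death and readmission, name a shorter list, for example age, ISS and organ grade. Say at what point ISS is scored.
4. Label the chi-squared, Fisher and t-tests of these outcomes as descriptive.
5. State that adjustment for admission severity does not remove confounding by the later clinical change that defines CC.

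The cost is a few sentences and a few more models. No new data are needed. The remaining weakness is limited adjustment for the rare outcomes.

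### Mortality, length of stay, transfusion, VTE prophylaxis and 30-day readmission are left to unadjusted tests that ignore site; only delayed complication and intervention get a mixed model

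*Supplement*

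**What the plan says.** All references are to the protocol in the Supplement.

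- *Data Collection and Statistical Analysis*, simple tests: "Categorical variables will be compared using Fisher's exact test or Chi-squared test. Continuous variables will be assessed using Student's t-test". They form the univariate half of a two-part plan: "Complications found on repeat imaging will be assessed using univariate and multivariate analysis".
- Same section, models: "a mixed effect multinomial logistic regression will be run with a binary outcome of whether the patient had a delayed complication", and "Another mixed effect multinomial logistic regression will be run with a binary outcome of whether the patient had an intervention performed". Neither sentence names the random effect or the covariates, and both call a model for a binary outcome multinomial. The estimates to be reported are these: "Data will be reported as adjusted odds ratios with 95% confidence intervals". The significance threshold is p<0.05.
- *Secondary Outcomes*: "Secondary Outcomes: Timing to repeat imaging/ intervention, interventions performed based on complications found, mortality, length of stay, blood transfusion requirements, VTE prophylaxis", followed by the 30-day readmission variables. Readmission is also Aim 4. Apart from intervention, no model is named for any of these. Timing of repeat imaging gets a further analysis whose method is not given.
- *Methods*: at least 5,000 subjects, 200 of them at the lead site, and "The number of subjects that will be enrolled at each additional participating site is 200".
- *Updated Terms/Definitions*: NCC imaging is "repeat imaging prompted by institutional protocol/ recommendations, individual physician practice pattern, or that performed on a scheduled basis". CC imaging is prompted by the patient's condition.
- *Background & Significance*: institutions are said to differ in, among other things, transfusion thresholds and follow-up imaging.

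**The concern.** A chi-squared, Fisher or Student's t-test treats every patient as an independent observation. That fails when the outcome and the comparison group both vary by hospital. The protocol gives reason to expect both: part of the NCC label comes from hospital policy, and transfusion practice is said to differ between hospitals.

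Case mix is a second problem. CC patients are re-imaged because something about them changed, so a crude comparison of mortality, stay or transfusion with NCC patients mixes the reason for the scan with its consequences.

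The study is meant to feed a management guideline. An unadjusted secondary result at p<0.05 could present a difference between hospitals, or between sicker and less sick patients, as a difference between imaging strategies.

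**Working it through.** **1. The plan's own figures.** The *Sample Size and Power Estimates* tables can be reproduced with the two-proportion formula for independent patients, two-sided alpha 0.05, 80% power, equal groups and no continuity correction:

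n per group = [1.96·√(2p̄(1−p̄)) + 0.84·√(p₁(1−p₁)+p₂(1−p₂))]² / (p₁−p₂)²

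For spleen, 0.47 v 0.42 gives 1,549.6, so 2 × 1,550 = 3,100. For liver, 0.20 v 0.27 gives 574.8, so 2 × 575 = 1,150. The other four rows (8,614; 1,582; 2,256; 696) also match exactly. The tables contain no allowance for clustering.

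**2. Clusters.** 5,000/200 = 25 sites (derived; the protocol does not state the number).

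The NCC/CC label exists only for re-imaged patients. Applying the pilot's re-imaging shares:
- Spleen: 3,500 × 105/235 ≈ 1,564, or about 63 per site.
- Liver: 1,500 × 122/365 ≈ 501, or about 20 per site.

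**3. Assumptions.** The documents give neither an outcome ICC nor the NCC share by site, so both are varied.
- Outcome ICC: 0.01, 0.02 and 0.05.
- Site mix: 9 sites with a high NCC share and 16 with a low one, chosen to keep the overall share near the pilot's spleen figure of 38/105 = 36%. The same mix is used for liver, where the pilot share was 50/122 = 41%.

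**4. Formula.** Design effect DE = 1 + (m−1) × ICC(outcome) × ICC(exposure). ICC(exposure) is the between-site variance of the NCC share divided by p(1−p). Actual type I error = 2[1 − Φ(1.96/√DE)].

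- Equal shares: ICC(exposure) = 0.
- Moderate, 60% v 22.5%: p = (9×0.60 + 16×0.225)/25 = 0.36. Variance = (9×0.24² + 16×0.135²)/25 = 0.0324. ICC(exposure) = 0.0324/0.2304 = 0.14.
- Strong, 85% v 9%: p = (9×0.85 + 16×0.09)/25 = 0.364. Variance = (9×0.4864² + 16×0.2736²)/25 = 0.133. ICC(exposure) = 0.133/0.231 = 0.58.

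Example (spleen, strong, ICC 0.05): DE = 1 + 62 × 0.05 × 0.575 = 2.78; 1.96/√2.78 = 1.175; type I error = 24%.

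**5. Type I error of an unadjusted chi-squared test at nominal 5%**

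| NCC share by site | Spleen, ICC 0.01 / 0.02 / 0.05 | Liver, ICC 0.01 / 0.02 / 0.05 |
|---|---|---|
| Equal | 5.0 / 5.0 / 5.0% | 5.0 / 5.0 / 5.0% |
| 60% v 22.5% | 6.0 / 7.1 / 10.2% | 5.3 / 5.6 / 6.6% |
| 85% v 9% | 9.2 / 13.4 / 24.0% | 6.3 / 7.6 / 11.5% |

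**6. Check by simulation.** I simulated null data with beta-distributed site rates, 25 equal sites and 20,000 runs per cell. At the pilot's complication rates (0.44 spleen, 0.25 liver) the results agree with the table to within about half a percentage point. With an assumed 5% event rate, nearer what a rarer outcome might show, the pattern is the same: spleen 6.1–9.9% (moderate) and 9.3–24.0% (strong); liver 5.2–6.2% and 6.0–11.1%. A site-stratified Mantel-Haenszel test stayed between 4.6% and 5.4% in every cell.

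These figures cover site clustering only. Bias from patient-level case mix comes on top and cannot be sized from the documents.

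**The case against.** The strongest reply is that the outcome that matters most is already handled. Right after the simple tests, the plan specifies mixed effect models for the primary outcome and for intervention. That stands, and it limits the point to the remaining secondary outcomes, plus the unnamed random effect in the two planned models.

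Two stronger readings are tempting, and the documents support neither.

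- A reader might infer that the planned confidence intervals are too narrow. The only intervals planned are for adjusted odds ratios, which come from the mixed models and not from the simple tests.
- A reader might infer that the imaging group is largely set by site protocol. Institutional protocol is one of three NCC triggers, beside individual physician practice and scheduled imaging. In the pilot most repeat imaging was discretionary (64% spleen, 59% liver). Those are overall shares and do not show how the mix varies between hospitals, so site dependence is plausible but unmeasured.

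It is also fair to say that inflation is not inevitable: with equal NCC shares across sites it vanishes, and the 85% v 9% mix is an upper-end scenario. The pilot rates used in the check are complication rates, an outcome the mixed model covers. The formula does not involve the event rate, however, and the 5% simulation gave similar results, so the range carries over to other binary outcomes given the same ICC. It was not worked out for length of stay or transfusion volume.

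Finally, the plan does not say outright that every secondary outcome will be compared between NCC and CC. The point applies to those that are.

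**Conclusion.** The point holds for mortality, length of stay, transfusion, VTE prophylaxis and 30-day readmission. Their only named analyses ignore site and case mix, although the protocol itself describes hospitals as differing in imaging and transfusion practice. For timing, the extra analysis is too little described to tell. Readmission matters most here, because it is a specific aim.

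At an assumed outcome ICC of 0.01–0.05, with 25 equal sites and the pilot's re-imaging shares, the true error rate of a nominal 5% chi-squared test would be:
- about 5% if sites do not differ in NCC share;
- about 6–10% (spleen) and 5–7% (liver) with a moderate difference;
- about 9–24% (spleen) and 6–11.5% (liver) with a strong one.

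This should be corrected before analysis. It does not undermine the planned model for the primary outcome, provided site is in fact its random effect.

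**What to change.** 1. State that site is the random intercept in the two planned models, list their case-mix covariates, and make those models the inferential analysis for complication and intervention. Call them binary logistic, not multinomial.
2. For every other secondary outcome to be compared between NCC and CC, specify a site-adjusted and case-mix-adjusted model suited to its type: logistic for mortality and readmission, and a form that tolerates skew and zeros for stay and transfusion. Say which method the timing analysis will use.
3. Keep the chi-squared, Fisher and t-tests as description, without significance claims.
4. Optionally, add each site's NCC proportion as a covariate, to separate within-site from between-site differences.

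The cost is a few paragraphs of text, some extra modelling and somewhat wider intervals. No new data are needed: the waiver of HIPAA section already assigns each site an identifier, and the age, injury severity, organ grade, vital signs and anticoagulant fields are in the data collection tool.
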